### **7.8.2 Secondary Efficacy Endpoint(s)**

The above analyses methodology and segmented summaries will be also applied to the following efficacy outcomes, at the end of the ENANTONE treatment and evaluated over time using the estimated study visits at 3-month intervals:

- Percentage of patients with peak LH suppression
- Percentage of patients with peak FSH suppression
- Percentage of patients with estradiol or testosterone level suppression to pre pubertal level
- Percentage of patients with a decrease from baseline in the ratio of bone age to chronological age only during treatment with ENANTONE

For each time point, a subject's peak LH (or FSH) value will be determined as largest value of the 0, 30, 60, 90 min samples from the stimulation test.

The abnormal values for a normal pediatric patient population in China for estradiol, testosterone, LH and FSH are listed in Table 2 below.

**Table 2 Criteria for Abnormal Values for Estradiol, Testosterone, LH and FSH**

Parameter	Unit	Gender	Lower Criteria	Upper Criteria
Estradiol	pg/mL		<0	>20
Testosterone	nmol/L		<0	>7.34
LH	U/L	Male	<0.3	>2.7
	U/L	Female	<0	>2.0
FSH	U/L	Male	<0	>3.7
	U/L	Female	<0.4	>6.7

Table 2 is used as a guideline to define Estradiol, Testosterone, LH, and FSH abnormal values in this study.

The determination of suppression to prepubertal levels of these hormones is a level less than or equal to the value in the upper criteria of this Table 2. Therefore, the cut-off value of suppression for each parameter is present in Table 3 below.

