10.4 Study Population

10.4.1 Inclusion Criteria

- 1) Subjects with diagnosis of idiopathic CPP
- 2) Subjects treated with leuprorelin acetate (ENANTONE) for at least 9 continuous months of therapy with either a stable dose of high dose ($\geq 90 \mu\text{g}/\text{kg}$ up to $180 \mu\text{g}/\text{kg}$) or low dose ($< 90 \mu\text{g}/\text{kg}$ down to $30 \mu\text{g}/\text{kg}$).
- 3) Subjects initiated and completed treatment during the index period from 1 September 1998 to 30 September 2018
- 4) Subjects who have the following information prior to initiation of ENANTONE and at least one record of each of the following parameters at the end of ENANTONE treatment in the medical records: Tanner staging, estradiol or testosterone level, and FSH and LH level. The subject should have at least one record of bone age prior to the initiation GnRHa therapy

with ENANTONE to support the diagnosis of CPP. In addition, the subject should have at least one record of bone age during treatment with ENANTONE.

5) The subject or, when applicable, the subject's legally acceptable representative signs and dates a written informed consent form and any required privacy authorization prior to the initiation of any study procedure

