### **5.2 Secondary Outcome**

1. LH and FSH suppression to prepubertal level during and after treatment with ENANTONE
2. Estradiol or testosterone level suppression to prepubertal level during and after treatment with ENANTONE
3. Decrease in the ratio of bone age to chronological age (BA/CA ratio) during treatment with ENANTONE

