#### **7.4 Demographic and Other Baseline Characteristics**

Patient demographics will be summarized using descriptive statistics on the safety analysis set. Individual subject demographics will be listed.

- Age at Date of Diagnosis of CPP (derived determining number of days between date of birth and date of diagnosis divided by 365.25 to obtain age in years).
- Age of appearance of secondary sexual characteristics
- Age at start of ENANTONE therapy
- Gender
- Family Origin from Northern or Southern China
- Height
- Weight
- BMI

The following baseline information prior to the initiation of ENANTONE therapy will be presented for this study as included in the analysis of the Change from Baseline in these parameters during the ENANTONE treatment period.

- Tanner Stage
- Random LH
- Random FSH
- LH and FSH for each time point during a GnRH stimulation test
- Peak LH during a GnRH stimulation test
- Peak FSH during a GnRH stimulation test

- Estradiol
- Testosterone
- Bone age
- Bone age/chronological age

The Bone age to Chronological age ratio is determined using birthdate and date of the bone age assessment to obtain age in days and then divided by 365.25 to obtain age in years, not truncated to an integer. Individual chronological age values will be reported to 1 decimal and mean values to 2 decimal places.

- Predicted Adult Height
- Bone Mineral Density (BMD)
- Linear growth rate
- Cranial CT or MRI

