**Table 3 Cut-off for Estradiol, Testosterone, LH and FSH suppression**

Parameter	Unit	Gender	Supression
Estradiol	pg/mL		$\leq 20$
Testosterone	nmol/L		$\leq 7.34$
LH	U/L	Male	$\leq 2.7$
	U/L	Female	$<2.0$
FSH	U/L	Male	$<3.7$
	U/L	Female	$<6.7$

These values above were also used to determine the peak LH and FSH suppression during a GnRH stimulation test. For this study the LH, suppression is defined as peak LH  $\leq 2$  U/L for female, and peak LH  $\leq 2.7$  U/L for male. For FSH, suppression is defined as peak FSH  $\leq 6.7$  U/L for female and  $0 \leq$  peak FSH  $\leq 3.7$  U/L for male.

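### SAP 7.8.2 takes upper limits for normal children in general as the cut-off for suppression to the prepubertal level, so the hormone responder percentages cannot be read as prepubertal suppression as written

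*SAP*

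**What the plan says.** **The outcome.** SAP 5.2 lists as its second secondary outcome "Estradiol or testosterone level suppression to prepubertal level during and after treatment with ENANTONE". LH and FSH suppression, also to the prepubertal level, is the first. Protocol 10.2.1 has the same outcomes. SAP 7.8.2 turns the second into a responder rate, "Percentage of patients with estradiol or testosterone level suppression to pre pubertal level", reported at the end of ENANTONE treatment and at 3-month intervals. It uses the exact confidence interval of SAP 7.8.1 and, under SAP 7.8, is shown for males, females and the total.

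**The reference values.** SAP 7.8.2 introduces them thus: "The abnormal values for a normal pediatric patient population in China for estradiol, testosterone, LH and FSH are listed in Table 2 below". Beneath the table it adds: "Table 2 is used as a guideline to define Estradiol, Testosterone, LH, and FSH abnormal values in this study". Neither place gives an age band or Tanner stage, and neither cites a source. SAP 8.0 has a reference list, but nothing ties any entry to Table 2.

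**The responder rule.** The next paragraph states: "The determination of suppression to prepubertal levels of these hormones is a level less than or equal to the value in the upper criteria" of Table 2. Table 3 then lists the cut-offs, and of the stimulated LH and FSH peaks the SAP says: "These values above were also used to determine the peak LH and FSH suppression during a GnRH stimulation test". The rule does not require the child to have been above the cut-off before treatment.

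**The concern.** The outcome names one population (prepubertal children) and the cut-off is described as coming from another (normal children, with no restriction). Nothing in the SAP connects the two. An upper limit of normal is built to flag abnormal values. If the reference group contains children in ordinary puberty, their values lie at or below the limit by design, and a treated child with the same value is scored as prepubertal.

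The label matters because little else in the analysis would show the problem. The SAP drops the dose comparison (SAP 7.13), so each result is an uncontrolled percentage whose height depends on the cut-off. The testosterone limit alone decides the sex-steroid result in the male column. The rule also runs into follow-up, where SAP 4.4 expects children to progress to puberty. A normal pubertal value in that phase could be reported as continued suppression. Protocol 13.0 intends the results for the regulator, to justify long-term use.

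**Working it through.** **1. Reproducing the cut-offs.** Applying the SAP rule (value ≤ Table 2 upper limit) to each row:

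| Hormone | Table 2 upper limit | Rule gives | Table 3 prints |
|---|---|---|---|
| Estradiol, pg/mL | 20 | ≤20 | ≤20 |
| Testosterone, nmol/L | 7.34 | ≤7.34 | ≤7.34 |
| LH male, U/L | 2.7 | ≤2.7 | ≤2.7 |
| LH female, U/L | 2.0 | ≤2.0 | <2.0 |
| FSH male, U/L | 3.7 | ≤3.7 | <3.7 |
| FSH female, U/L | 6.7 | ≤6.7 | <6.7 |

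All six numbers agree, so Table 3 is Table 2 relabelled and no separate prepubertal limit enters. The strict inequalities in the last three rows differ from the rule and from the text under Table 3. That is a side matter and does not affect this point.

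**2. The two populations side by side.** Table 2 is described as applying to normal children in China. The rule calls the same limits prepubertal. Protocol 8.0 defines precocity as onset before 9 years in boys and before 8 in girls. Puberty that begins later, still in childhood, is therefore not precocious. A normal paediatric group with no age or stage restriction would ordinarily include such children. This is an inference: the SAP neither says that they were included nor that they were excluded.

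**3. Units.** The molar mass of testosterone is 288.4 g/mol (a physical constant, not from the documents). 7.34 nmol/L × 288.4 ng/nmol = 2,117 ng/L = 211.7 ng/dL, about 212 ng/dL.

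**4. Share of boys at or below the cut-off if the drug did nothing.** The documents give no baseline testosterone values, so this is a range over assumptions. Let baseline be lognormal with median m and log-scale SD s. Then the share is q0 = Φ[(ln 7.34 − ln m)/s]. Example: m = 2, s = 0.8 gives (ln 3.67)/0.8 = 1.300/0.8 = 1.63, so q0 = 94.8%. For s from 0.5 to 1.2:

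| Assumed median m, nmol/L | q0 |
|---|---|
| 1 | 95 to 100% |
| 2 | 86 to 99.5% |
| 4 | 69 to 89% |
| 7.34 | 50% |
| 10 | 27 to 40% |
| 15 | 8 to 28% |

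**5. How far the drug can move the rate.** Suppose boys already at or below the cut-off stay there, and the drug brings a share e of the others below it. The reported rate is R = q0 + (1 − q0) × e.

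- q0 = 0.25: R runs from 25% (e = 0) to 0.25 + 0.75 × 0.95 = 96% (e = 0.95).
- q0 = 0.90: R runs from 90% to 0.90 + 0.10 × 0.95 = 99.5%.

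The percentage is informative in the first case and nearly fixed in the second. The documents do not say which applies. Entry requires records of "Tanner staging, estradiol or testosterone level, and FSH and LH level" before and at the end of treatment (Protocol 10.4.1), with no minimum hormone level.

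**The case against.** **The table may in fact be prepubertal.** Silence about stage does not prove that pubertal children were in the reference group, and the rule itself uses the word prepubertal. This stands to the extent that the finding must be worded as *may*. One citation could settle it. Until it is given, the only description of the population in the SAP points the other way.

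**Readers will see the underlying values.** SAP 7.4 says "The following baseline information prior to the initiation of ENANTONE therapy will be presented for this study", and its list includes estradiol and testosterone. SAP 7.10 summarises hormone measurements by phase, and SAP 7.8 lists individual data. This is a real mitigation, since a careful reader could re-score the children. It does not correct the percentage that will be reported under the prepubertal label.

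**The stakes are limited.** These are secondary outcomes in a study that Protocol 10.9 calls unpowered for hypothesis testing. With the dose comparison gone, the argument that a lenient cut-off would hide incomplete suppression at low doses has little force. Both points stand. Single rows for estradiol and testosterone are not a fault either, because Protocol 10.2.2.9 records the first in girls and the second in boys.

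**Stronger readings that the documents do not support.** A reader might infer that the male testosterone rate will be close to 100% whatever the drug does. That needs nearly all boys to start at or below 7.34 nmol/L, and steps 4 and 5 show that it depends wholly on an assumed baseline. A reader might also infer that 7.34 nmol/L is some definite multiple of the proper limit. The documents contain no prepubertal testosterone limit, so any such multiple only restates the limit assumed.

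**Conclusion.** The concern holds in a limited form. SAP 7.8.2 defines suppression to the prepubertal level by limits that it describes as separating normal from abnormal in children generally, with no source, age band or stage. As written, the responder percentages cannot be read as prepubertal suppression, and they may be overstated both on treatment and in follow-up. The labelling fault covers every row of Table 2. Testosterone at ≤7.34 nmol/L (212 ng/dL) is the entry most in need of checking; no size was worked out for estradiol, LH or FSH.

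The size of any overstatement is unknown. The range of about 8% to 100% for boys at or below the testosterone cut-off with no drug effect rests on assumed lognormal baselines with medians of 1 to 15 nmol/L and log-scale SDs of 0.5 to 1.2. The number of boys among the roughly 100 subjects (SAP 6.0) is also not stated, so the effect on the total row cannot be given. For secondary outcomes this is something that should be corrected; it does not undermine the study.

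**What to change.** 1. Check every Table 2 entry against its source, and 7.34 nmol/L in particular for unit, decimal place and population. Cite the source in SAP 7.8.2.
2. Replace the limits in Tables 2 and 3 with upper limits from one named prepubertal (Tanner I) paediatric source, applied to the recorded hormone values. One common source is preferable to each laboratory's own range: reference ranges are not among the variables listed in Protocol 10.2.2.9, and with eight facilities and a 1998 to 2018 index period the definition of response would vary.
3. If only all-paediatric limits are available, label the result *within the normal paediatric range* and do not report it as suppression to the prepubertal level.
4. For each hormone, report the share already at or below the cut-off at baseline, among subjects with a value inside the 93-day window of SAP 7.1.1.

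**Cost.** SAP wording, two tables, a reprogrammed responder flag and one added baseline line. No new data need be collected. The downside is that the suppression percentages may become less favourable.

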**Table 3 Cut-off for Estradiol, Testosterone, LH and FSH suppression**

Parameter	Unit	Gender	Supression
Estradiol	pg/mL		$\leq 20$
Testosterone	nmol/L		$\leq 7.34$
LH	U/L	Male	$\leq 2.7$
	U/L	Female	$<2.0$
FSH	U/L	Male	$<3.7$
	U/L	Female	$<6.7$

These values above were also used to determine the peak LH and FSH suppression during a GnRH stimulation test. For this study the LH, suppression is defined as peak LH  $\leq 2$  U/L for female, and peak LH  $\leq 2.7$  U/L for male. For FSH, suppression is defined as peak FSH  $\leq 6.7$  U/L for female and  $0 \leq$  peak FSH  $\leq 3.7$  U/L for male.

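### SAP 7.8.2 narrows the LH/FSH suppression outcome to the stimulated peak, which eligibility does not require, and gives no basis for applying the Table 2 limits to it

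*SAP*

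**What the plan says.** Protocol 10.2.1 and SAP 5.2 set the first secondary outcome as LH and FSH reaching a prepubertal level. Protocol 10.7.3 analyses it as the percentage of patients with LH suppression and, separately, with FSH suppression. None of these sections restricts the outcome to a stimulated value.

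SAP 7.8.2 lists two LH/FSH endpoints, both on the peak. The "peak LH (or FSH) value will be determined as largest value of the 0, 30, 60, 90 min samples" of the stimulation test. The limits come from Table 2, introduced as follows: "The abnormal values for a normal pediatric patient population in China for estradiol, testosterone, LH and FSH are listed in Table 2 below". Suppression is then "a level less than or equal to the value in the upper criteria of this Table 2". Below Table 3 the SAP adds "These values above were also used to determine the peak LH and FSH suppression during a GnRH stimulation test" and fixes the operative rule, beginning "For this study the LH, suppression is defined as peak LH": at most 2 U/L (female) or 2.7 U/L (male) for LH, and at most 6.7 U/L (female) or 3.7 U/L (male) for FSH.

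For hormones, Protocol 10.4.1 (repeated in SAP 4.4) asks for values before treatment and "at least one record of each of the following parameters at the end of ENANTONE treatment". The list names an estradiol or testosterone level and an FSH and LH level. It does not name a stimulation test.

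SAP 7.13 reports one departure from the protocol: the low-versus-high dose comparison and its Cochran-Mantel-Haenszel test are dropped.

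**The concern.** Three things do not fit together.

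- **Coverage.** The outcome is stated for LH and FSH in general, but the analysed rate needs a test that a subject can be eligible without. In a chart review of about 100 subjects (SAP 6.0), the LH/FSH result could rest on an unknown and possibly selected subset, namely those whose physicians chose to run a stimulation test on treatment.
- **Cut-off.** A limit described only as relating to normal children is applied to the largest of four samples after a stimulus. The SAP does not say whether Table 2 holds random, basal or stimulated values, or why one number serves both uses.
- **Disclosure.** A reader of SAP 5.2 and 7.13 would not learn that the outcome had been narrowed.

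At stake is what the reported percentage means and whom it describes. No hypothesis test depends on it.

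**Working it through.** **Step 1. Stated outcome against analysed endpoint.**

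| Place | LH/FSH quantity |
|---|---|
| Protocol 10.2.1, SAP 5.2 | suppression to prepubertal level, sample type not stated |
| Protocol 10.7.3 | percentage with LH (FSH) suppression, sample type not stated |
| SAP 7.4 | random and peak LH/FSH listed as separate variables |
| SAP 7.8.2 | percentage with peak suppression only |
| Protocol 10.4.1, SAP 4.4 | an LH and FSH level required; no stimulation test required |

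Under 7.8.1, whose method 7.8.2 adopts, the end-of-treatment value is the last observation in the treatment phase. A subject therefore needs at least one stimulation test in that phase to have a peak at all, and one in each window to appear in the 3-monthly rates. A subject with only unstimulated values meets the eligibility rule and has no peak. Section 7.8.2 gives no denominator rule for such subjects. The documents do not say how many there will be.

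**Step 2. Direction of the difference.** Write X0, X30, X60 and X90 for the four samples and c for the limit. The peak is max(X0, X30, X60, X90), so peak ≤ c implies X0 ≤ c. In the same subjects, P(peak ≤ c) ≤ P(X0 ≤ c). This follows from the SAP's definition and needs no outside source. (Protocol 10.2.2.14 also records a 120-minute sample, which the SAP peak leaves out. The direction is the same either way.)

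**Step 3. Size, as illustration only.** Assumptions that are in neither document: log-values are exchangeable normal with common correlation ρ, and 90% of single samples lie at or below c.

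Formula: P(peak ≤ c) = E[ Φ( (z − √ρ·U) / √(1−ρ) )⁴ ], with z the 90th normal percentile and U standard normal. At ρ = 0 this is 0.9⁴ = 0.656. At ρ = 1 it is 0.90. Values in between are by simulation.

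| ρ | No stimulated rise | 0.5 SD rise at 30–90 min |
|---|---|---|
| 0 | 66% | 43% |
| 0.5 | 74% | 57% |
| 0.8 | 81% | 66% |
| 0.95 | 86% | 73% |
| 1 | 90% | 78% |

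Four samples from one child within 90 minutes will not be independent, so the first row is a bound and not an estimate.

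**Step 4. Table 3 against its own rule.** Applying the at-or-below rule to the Table 2 upper limits:

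| Parameter | Rule gives | Table 3 prints |
|---|---|---|
| Estradiol | ≤ 20 | ≤ 20 |
| Testosterone | ≤ 7.34 | ≤ 7.34 |
| LH male | ≤ 2.7 | ≤ 2.7 |
| LH female | ≤ 2.0 | < 2.0 |
| FSH male | ≤ 3.7 | < 3.7 |
| FSH female | ≤ 6.7 | < 6.7 |

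All six numbers agree, and three of the six signs do not. Only values exactly on a limit are affected. With 90 of 100 suppressed under ≤ (90%, Clopper-Pearson 95% CI 82.4 to 95.1), one tie under < gives 89% (81.2 to 94.4) and five ties give 85% (76.5 to 91.4).

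**The case against.** The strongest reply is that a stimulated peak is a legitimate endpoint and the SAP is explicit about choosing it. That stands: nothing here argues for removing the peak.

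Next, incomplete data are foreseen. Outcomes are reported on available data without imputation (Protocol 10.3, 10.9), and missing data are not a deviation (Protocol 10.8.2, SAP 7.3). This excuses gaps in the data. It does not state the denominator, and it does not explain leaving unused the LH/FSH values that eligibility asks for.

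Random values are also not ignored: SAP 7.4 includes random LH and FSH in the change-from-baseline analysis, and 7.10 summarises hormone measurements by phase. Neither gives a percentage suppressed, which is what the protocol outcome calls for.

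The eligibility rule does not say that the LH and FSH level must be unstimulated, so an unstimulated value is not guaranteed either. That is correct. It is why the added rate should accept a random value or the 0-minute sample and be restricted to subjects who have one.

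A reader might also infer that the peak rate is biased against suppression. The documents do not support this. It would be bias only if Table 2 held unstimulated limits and unstimulated suppression were the target. The word also in "These values above were also used to determine the peak LH and FSH suppression during a GnRH stimulation test" hints at the first, but the SAP does not say so.

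**Conclusion.** The point holds in this form: the LH/FSH suppression endpoint is narrower than the outcome it serves, the narrowing is not recorded in SAP 7.13, and the limit applied to the peak has no stated basis. These conclusions rest on the documents' text. That the peak rate cannot exceed the 0-minute rate follows from the definition of the peak. The illustrative 66% to 90% depends entirely on the assumed 90% rate, the normal model and the correlation, and must not be read as an expected loss.

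Two stronger readings should be set aside. A reader might infer that random and peak suppression rates will be reported side by side and are not comparable, but no random-value suppression rate is planned. A reader might also infer from Table 3 that suppression is not uniquely defined, but at-or-below is stated before the table and again beneath it, so the intended rule is clear and the three strict signs are an editorial slip.

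The importance is moderate: this is a secondary outcome in a descriptive study that is not powered for testing (Protocol 10.9), but the correction is cheap.

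**What to change.** - **SAP 7.8.2, add:** the percentage of subjects with unstimulated LH, and with unstimulated FSH (random value, or the 0-minute sample), at or below the Table 2 limit, with Clopper-Pearson 95% CIs, for all subjects with such a value, and with the denominator shown.
- **SAP 7.8.2, keep:** peak suppression as a separate result among subjects with a stimulation test. Show its denominator and state the basis of its cut-off. If there is no basis to state, summarise the peak as a continuous variable.
- **SAP 7.13:** record that the protocol outcome was narrowed to the peak, and how the added rate restores it.
- **Table 3 (minor):** check the original table, since a lost underline would produce the same signs. If they are as printed, change female LH, male FSH and female FSH to ≤.

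The cost is SAP wording and one added table. LH and FSH levels and the 0-minute sample are already among the variables to be collected (Protocol 10.2.2.9 and 10.2.2.14), and random LH and FSH are already SAP variables (7.4).

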### **7.8.3 Additional Efficacy Endpoint(s)**

Percent of patients with a change from baseline in the following parameters will be summarized in a similar manner as the above categorical secondary efficacy endpoint:

- Increase in predicted adult height during and after treatment with ENANTONE
- Change from baseline for BMI
- Change from baseline in BMD
- Change from baseline in patient height

For these and the other additional efficacy endpoints, descriptive statistics will be provided without inferential comparisons for the end of ENANTONE treatment phase and 3-month intervals and follow-up segments previously described.

- Increase in predicted adult height during and after treatment with ENANTONE
- Change from baseline in standard laboratory tests during and after treatment with ENANTONE
- Incidence rate of polycystic ovarian syndrome during and after treatment with ENANTONE
- Evaluation of long term effect on reproduction
- Change from baseline for BMI

- Change from baseline in BMD
- Change from baseline in patient height

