8.0 RATIONALE AND BACKGROUND

Precocious puberty refers to appearance of secondary sexual characteristics in boys before 9 years and girls before 8 years [1]. Children with CPP have premature secretion and release of GnRH in the hypothalamus, activating secretion of gonadotropin by the pituitary gland, promoting development of the gonads and secretion of sex hormones, resulting in development of internal and external genital organs and appearance of secondary sexual characteristics [1]. Treatment goals include hormonal suppression, cessation of development of secondary sex characteristics, halting or preventing menarche, and preservation of adult height [1][2]. If left untreated, children with CPP can also face psychological challenge resulting from premature physical maturation that contrasts with their immature emotional development [2].

GnRHa have been the standard of care for CPP [1]. Continuous exposure to GnRHa desensitizes pituitary gonadotropin receptors and suppresses LH and FSH secretion [2].

ENANTONE is a GnRHa widely used in the treatment of CPP. It was approved for CPP indication in China in 1998 at the dose of 30-90 µg/kg body weight subcutaneously administration every 4 weeks. However, recent clinical studies demonstrated that administration of leuprorelin acetate at lower than 90 µg/kg body weight cannot achieve optimal pituitary desensitization in many patients. If incomplete suppression is operative during treatment, GnRHa administration may exacerbate disease progression and bone age increase, impairing long-term outcome [3]. The dose greater than 90 µg/kg body weight was recommended in CPP treatment guideline issued in 2010 by the Ministry of Health of China and Consensus on Diagnosis and Treatment of Central Precocious Puberty (2015) [4][5].

In 2013, CFDA approved the new dose of leuprorelin acetate at 30-180 µg/kg body weight, SC, every 4 weeks [6]. The approval was based on results from the clinical trials of leuprorelin acetate conducted in US and Europe and a retrospective study in Japan [7][8]. There is a lack of safety and effectiveness data of leuprorelin acetate long term use in China. This retrospective, medical chart review study is designed to evaluate and compare descriptively the effectiveness and safety of high dose (≥ 90 µg/kg up to 180 µg/kg) and low dose (< 90 µg/kg down to 30 µg/kg) leuprorelin acetate in China.

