10.2.2.4 BMD

The z-score for BMD and the anatomical site of measurement will be recorded. The BMD is typically determined using dual-energy X-ray absorptiometry, but BMD determined with any apparatus/mode is acceptable for collection.

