10.2.2.6 Height, Predicted Adult Height, Weight and BMI

Height, predicted adult height and weight will be recorded.

The predicted adult height is preferably derived by the Tanner-Whitehouse 3 method; where not possible, Bayley-Pinneau method or other methods are also acceptable.

The BMI will be calculated by the sponsor from the patient's weight and height recorded in the CRF. The calculated BMI results will not be recorded in the CRF.

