#### 7.1.1 Study Definitions of Baseline and Change from Baseline

Baseline, for the ENANTONE period, is defined as the last non-missing measurement prior to the first dose of ENANTONE treatment. Unless specified otherwise, baseline values for variables related to CPP will be limited to values collected no more than 3 months (93 days), inclusive, prior to the first dose of ENANTONE.

The change from baseline will be calculated for the treatment period by subtracting the baseline values from the individual post-baseline values. If either the baseline or post-baseline value is missing, the change from baseline is set to be missing as well.

Data from the follow-up period after completion of treatment period, will be analyzed separately and the baseline for the follow-up period will be defined as the first non-missing measurement after the last dose of GnRHa treatment (with either ENANTONE or another GnRHa).

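### SAP 7.8.3 counts patients with a change in BMI, BMD and height without stating a direction, and summarises height and BMI change in growing children on the raw scale only

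*SAP*

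**What the plan says.** SAP 7.8.3 plans two summaries of the same variables.

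- **A percentage.** "Percent of patients with a change from baseline in the following parameters will be summarized" in the manner of the categorical secondary endpoints, that is, a proportion with a Clopper-Pearson interval (SAP 7.8.1 and 7.8.2). The list holds predicted adult height, BMI, BMD and patient height. Only predicted adult height has a direction (increase). The height entry reads "Change from baseline in patient height", and the BMI and BMD entries have the same form.
- **Descriptive statistics.** For the same variables, "descriptive statistics will be provided without inferential comparisons for the end of ENANTONE treatment phase and 3-month intervals", and also for the follow-up segments. SAP 7.1 sets mean, SD, median, minimum and maximum, for males, females and total.

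SAP 7.1.1 obtains change "by subtracting the baseline values from the individual post-baseline values", so it is signed and in the units of the variable. On scale, Protocol 10.2.2.6 says "Height, predicted adult height and weight will be recorded" and "The BMI will be calculated by the sponsor from the patient's weight and height recorded in the CRF". Neither document mentions an SDS, percentile or age adjustment for height or BMI. For BMD, by contrast, Protocol 10.2.2.4 says "The z-score for BMD and the anatomical site of measurement will be recorded".

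**The concern.** There are two separate problems.

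First, the percentage has no defined event for BMI, BMD or height. If any difference counts, an increase and a decrease score the same. If a direction was intended, someone must choose it at programming, possibly with the data in view.

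Second, the patients are children whose disease is defined by "appearance of secondary sexual characteristics in boys before 9 years and girls before 8 years" (Protocol 8.0). Height rises with age and BMI may do so. SAP 7.7 tabulates treatment durations from 9 months to 60 months and beyond, so the end-of-treatment summary pools raw changes over very different lengths of growth. The 3-month windows fix the interval but not the child's age. There is no untreated group, and SAP 7.13 drops the dose comparison. Nothing inside the study therefore shows what change to expect without treatment.

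At stake is the reading of BMI change, a listed outcome, in a report that Protocol 13.0 says will go to the regulator to support long-term use.

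**Working it through.** **1. Figures in the documents.** None concerns BMI, BMD or height. The only precision figures (Protocol 10.5) are for Tanner response with 150 per dose group: 1.96 × √(0.75 × 0.25/150) = 6.9% and 1.96 × √(0.85 × 0.15/150) = 5.7%, with odds ratio 1.89 (95% CI 1.06 to 3.38). They reproduce the stated 7%, 6% and lower bound above 1, but do not bear on this point.

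**2. Is a direction given anywhere?**

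| Variable | SAP percentage | Protocol 10.7.3 |
|---|---|---|
| BA/CA ratio | decrease (7.8.2) | percentage, decrease |
| Predicted adult height | increase (7.8.3) | percentage, increase |
| BMI, BMD, height | none (7.8.3) | quantitative change only |

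The percentage for the last row is new in the SAP. SAP 7.13 does not list it as a change.

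**3. Percentage with any change.** The documents give no growth figures, so all inputs here are assumptions. Let the true change be normal with mean μ and SD σ, and the recording step be r. Then

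P(any change) = 1 − [Φ((r/2 − μ)/σ) − Φ((−r/2 − μ)/σ)], and P(increase) = 1 − Φ((0.05 − μ)/σ).

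*Height.* Growth v = 3 to 7 cm/year, between-child SD 1 cm/year, measurement error SD 0.5 cm per reading. Over t years, μ = vt and σ = √(t² + 2 × 0.5²).

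- Lowest case at 9 months: v = 3, t = 0.75, so μ = 2.25 and σ = √(0.5625 + 0.5) = 1.03.
 - r = 0.1 cm: P(any change) = 99.6%.
 - r = 1 cm: P(any change) = 95.9%.
 - P(increase) = 98.4%.
- At v = 7 all three are 100.0% to one decimal.
- The range from 9 months on is therefore 99.6 to 100% (r = 0.1 cm) or 96 to 100% (r = 1 cm). A more than twofold difference in growth rate moves the percentage by at most about 4 points.
- At 3 months it is less extreme: 97 to 99.6% (r = 0.1 cm) or 68 to 95% (r = 1 cm).
- If all of 100 subjects change, the Clopper-Pearson interval is 0.025^(1/100) = 96.4% to 100%.

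*BMI.* Derived to 0.1 kg/m², SD of change 0.7 to 1.5. With zero drift (μ = 0), P(any change) is 94.3% at σ = 0.7 and 97.3% at σ = 1.5.

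**4. Raw signed change with no treatment effect.**

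- Height: mean change is 3 × 0.75 = 2.25 to 7 × 0.75 = 5.25 cm at 9 months, and 3 × 2 = 6 to 7 × 2 = 14 cm at 2 years, from growth alone.
- BMI: with an age drift of 0.2 to 0.6 kg/m² per year over 2 years, μ = 0.4 to 1.2. P(increase) runs from 59.2% (μ = 0.4, σ = 1.5) to 95.0% (μ = 1.2, σ = 0.7) with no shift in BMI for age. With zero drift it is 47 to 49%.

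**5. BMD.** It is recorded as a z-score, so step 4 does not apply to it. The missing direction does.

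**The case against.** A reader might infer that both summaries are uninformative, that the results will mostly show normal growth, or that excess weight gain and growth loss cannot be seen. The documents do not support readings that strong.

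- The descriptive statistics are signed, given by sex and every 3 months, and include the maximum. A large BMI gain would show. What is missing is a reference against which to judge it.
- Age-referenced growth information is already planned. BA/CA is a secondary outcome and predicted adult height an additional one, both with a direction.
- For BMI, the share of raw change that is expected growth depends on a drift the documents do not give. Across the assumed values the proportion increasing runs from just under half to 95%.
- Counting any difference is one reading. The first item in the same list is directional, so the wording may simply be incomplete. That lowers the cost of repair but leaves the event undefined.
- Protocol 10.9 already states that the study is non-randomised, unpowered and descriptive. SDS would not supply a control group.
- Protocol 10.7.3 specifies change in BMI and height, so raw change should not be displaced. SDS for chronological age need not average zero change in children selected for early puberty.

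All of these stand as limits on size or on the form of the fix. None supplies a direction for the percentage, or an age and sex reference for height and BMI. The baseline covariate in Protocol 10.7.3 does not supply that reference either: it would not remove growth with age, and the SAP contains no such model.

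**Conclusion.** The point holds in two parts. The percentage for BMI, BMD and height lacks a defined event. Taken literally, it is near 100% for height from 9 months on (96 to 100% under the assumed growth rates and recording steps) and at least 94% for BMI even with no drift. It therefore carries almost no information about treatment. The signed height and BMI statistics are informative but raw only, so they cannot readily be told apart from expected growth. This is clear for height; for BMI its extent is an assumption. The raw-scale part does not extend to BMD. The impact is modest: BMI is an additional outcome (Protocol 10.2.1, SAP 5.3), and patient height is in neither outcome list although it is analysed. The change should be made, but the primary and secondary results do not depend on it.

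**What to change.** In SAP 7.8.3:

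1. Delete the percentage for BMI, BMD and patient height, or give each a stated direction, for example the percentage with an increase in BMI SDS and the percentage with a decrease in BMD z-score.
2. Keep the raw change that Protocol 10.7.3 specifies. Beside it, add change in age- and sex-specific height SDS and BMI SDS from one growth reference named before analysis, with 95% CI, for the same time points and follow-up segments.
3. Record in SAP 7.13 whatever percentage is kept for these variables, since Protocol 10.7.3 has none.

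The cost is SAP wording and one derivation. Date of birth and sex (Protocol 10.2.2.2) and height and weight (Protocol 10.2.2.6) are already collected. The downsides are that a reference must be chosen for data spanning 1998 to 2018, and that SDS for chronological age must be read with caution in early puberty and do not replace a control group. The report should say so.
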